8.5.4. Clinical Laboratory Findings

Clinical laboratory variables will be presented in two ways. First, the mean change from baseline to each scheduled visit will be summarized. Second, the number and percent of participants with treatment-emergent potentially clinically significant (PCS) laboratory values will be tabulated. Treatment-emergent PCS laboratory tests are those in which the baseline value is normal and post-baseline value is abnormal (i.e., meets Grade III or Grade IV toxicity criteria from the NCI-CTCAE Version 5 or higher). Baseline will be defined as the last value obtained before receiving study drug.

No formal statistical tests will be performed.

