7.2 CLINICAL LABORATORY PARAMETERS

Laboratory assessments include hematology, clinical chemistry, and iron indices:

- Hematology: Hgb, Hct, RBC, WBC, MCV, MCH, MCHC, RDW, platelets, differential

count, reticulocyte count and CHr

- Clinical chemistry: sodium, potassium, chloride, BUN, creatinine, albumin, alkaline phosphatase, total bilirubin, GGT, AST, ALT, LDH, calcium, phosphorus, glucose, bicarbonate and magnesium.
- Iron indices: serum iron, serum ferritin, and total iron binding capacity (TIBC), and percentage serum transferrin saturation (TSAT).
- Other: Serum pregnancy test

All laboratory parameters will be presented in conventional units. The actual value and mean change from baseline to each scheduled visit will be summarized using descriptive statistics for each laboratory test group above.

Time course table for serum phosphate will be constructed for subjects in safety population. Descriptive statistics of days to first value of specified CTC grade and days to return to normal will be summarized. Only the subjects with a normal serum phosphate baseline value will be included in this table.

The number and percent of subjects with treatment-emergent potentially clinically significant (PCS) laboratory values after baseline will be summarized by visit. The denominator is all subjects with normal baseline and at least one post baseline assessment in the safety population and the numerator is the number of subjects with PCS (i.e., meets Grade 3 or Grade 4 AE scale defined in Division of AIDS (DAIDS) Table for Grading the Severity of Adult and Pediatric Adverse Events, Version 2.1 from March 2017 (Division of AIDS, National Institute of Allergy and Infectious Diseases, National Institutes of Health, US Department of Health and Human Services)) at any post-baseline visit.

Shift from baseline AE grade to maximum post-baseline AE grade, and shift from baseline to the last visit in terms of AE grade will be summarized, separately.

The AE grade for Chemistry and Hematology are defined in Appendix 1.1. BUN, hematocrit, bands and iron indices do not have adverse event scales available and are not evaluated separately as possible AEs.

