PARAMETER	GRADE 1 MILD	GRADE 2 MODERATE	GRADE 3 SEVERE	GRADE 4 POTENTIALLY LIFE-THREATENING
Absolute Neutrophil Count (ANC), Low (cells/mm3; cells/L) > 7 days of age	800 to 1,000 0.800×10^9 to 1.000×10^9	600 to 799 0.600×10^9 to 0.799×10^9	400 to 599 0.400×10^9 to 0.599×10^9	< 400 $< 0.400 \times 10^9$
Hemoglobin, Low (g/dL; mmol/L) ≥ 13 years of age (male only)	10.0 to 10.9 6.19 to 6.76	9.0 to < 10.0 5.57 to < 6.19	7.0 to < 9.0 4.34 to < 5.57	< 7.0 < 4.34
≥ 13 years of age (female only)	9.5 to 10.4 5.88 to 6.48	8.5 to < 9.5 5.25 to < 5.88	6.5 to < 8.5 4.03 to < 5.25	< 6.5 < 4.03
57 days of age to < 13 years of age (male and female)	9.5 to 10.4 5.88 to 6.48	8.5 to < 9.5 5.25 to < 5.88	6.5 to < 8.5 4.03 to < 5.25	< 6.5 < 4.03
Platelets, Decreased (cells/mm3; cells/L)	100,000 to < 125,000 100.000×10^9 to < 125.000×10^9	50,000 to < 100,000 50.000×10^9 to < 100.000×10^9	25,000 to < 50,000 25.000×10^9 to < 50.000×10^9	< 25,000 $< 25.000 \times 10^9$
WBC, Decreased (cells/mm3; cells/L) > 7 days of age	2,000 to 2,499 2.000×10^9 to 2.499×10^9	1,500 to 1,999 1.500×10^9 to 1.999×10^9	1,000 to 1,499 1.000×10^9 to 1.499×10^9	< 1,000 $< 1.000 \times 10^9$

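### The PCS laboratory table leaves out worsening from an abnormal baseline; shift tables recover it only for parameters graded in Appendix 1.1, which omits phosphorus, and the Hgb row will be sparse or empty

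*SAP*

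**What the plan says.** Protocol 8.5.4 puts the restriction into the definition: "Treatment-emergent PCS laboratory tests are those in which the baseline value is normal and post-baseline value is abnormal", where abnormal means NCI-CTCAE Grade 3 or 4. SAP 7.2 keeps it and applies it to the denominator: "The denominator is all subjects with normal baseline and at least one post baseline assessment". A child enters the numerator if a post-baseline value "meets Grade 3 or Grade 4 AE scale defined in Division of AIDS (DAIDS) Table". SAP Section 9 records the switch from CTCAE to DAIDS but leaves the normal-baseline rule as the protocol has it.

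The next paragraph of SAP 7.2 plans two further outputs with no baseline limit: "Shift from baseline AE grade to maximum post-baseline AE grade, and shift from baseline to the last visit in terms of AE grade will be" tabulated. On the scale to use, it says: "The AE grade for Chemistry and Hematology are defined in Appendix 1.1". It adds that BUN, hematocrit, bands and iron indices have no scale.

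SAP 7.2 also plans a time-course table for serum phosphate, restricted to children whose baseline phosphate is normal. SAP 7.1.1 names hypophosphatemia among the adverse events of special interest (AESI).

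Baseline is the last value before the first dose (SAP 2.3.1). Protocol 4.2.1 requires Hgb below 11 g/dL at entry. Neither document says whether a normal baseline means within the laboratory's reference range or ungraded on the DAIDS scale. Appendix 1.1 prints no reference limits for Hgb or phosphorus.

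**The concern.** A new Grade 3 or 4 value in a child who started at Grade 1 or 2 has emerged on treatment, yet the PCS table drops that child from numerator and denominator alike. This population is selected for abnormal blood values, so the excluded children are numerous for Hgb, and they start nearest the Grade 3 threshold. The trial enrolls at most about 36 children and has no data and safety monitoring board (SAP 8.2), so a single uncounted severe value matters to the safety description. The question is whether another planned table picks these children up, and for which analytes.

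**Working it through.** The documents give no event rate or sample size calculation for this point, so there is no stated figure to reproduce. The check compares the planned tables.

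**1. Where a post-baseline Grade 3-4 value is counted (parameter graded in Appendix 1.1)**

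| Baseline | PCS table | Shift tables |
|---|---|---|
| Normal | counted | shown |
| Grade 1-2 | not counted | shown |
| Grade 3, then Grade 4 | not counted | shown |

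**2. Which parameters the shift tables can cover**

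- SAP 7.2 lists 17 chemistry analytes.
- Appendix 1.1 grades 8: albumin, alkaline phosphatase, ALT, AST, calcium, creatinine, potassium and sodium. It also grades ANC, Hgb, platelets and WBC.
- 17 − 8 = 9 chemistries have no scale. BUN is declared to have none available, so 9 − 1 = 8 are left unexplained: phosphorus, magnesium, total bilirubin, glucose, bicarbonate, GGT, LDH and chloride.

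**3. Phosphorus: a child with low baseline phosphate who falls to Grade 3-4**

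- PCS table: excluded by the normal-baseline rule if the full DAIDS table is applied. If only Appendix 1.1 is applied, phosphorus has no grade and no PCS count at all.
- Time-course table: excluded by its own normal-baseline rule.
- Shift tables: no phosphorus grade to use.
- Summaries by visit: the minimum may reflect the value, but they do not count children who worsened.
- Adverse event tables, including the AESI search: counted only if the investigator judged the change a clinically significant worsening and recorded it (protocol 7.1).

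**4. The Hgb row**

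*If normal means a reference range with a lower limit at or above 11 g/dL*, the denominator is about 0 of 36. The exception is a child whose Day 0 pre-dose value, which is the baseline, is back at or above that limit.

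*If normal means ungraded*, the Grade 1 cells of Appendix 1.1 (g/dL, then mmol/L) decide:

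- Males aged 13 or over: "10.0 to 10.9 6.19 to 6.76". Every value below 11 is graded, so none enter.
- Females aged 13 or over and all children under 13: "9.5 to 10.4 5.88 to 6.48". Values of 10.5 to 10.9 are ungraded and enter.

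Assumption, not in the documents: Hgb is normal with mean μ of 9.0 to 10.5 and SD σ of 0.8 to 1.2, truncated below 11 and recorded to 0.1. The ungraded share is

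[Φ((10.95 − μ)/σ) − Φ((10.45 − μ)/σ)] / Φ((10.95 − μ)/σ).

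- Lowest: μ = 9.0, σ = 0.8 gives 0.028, and 36 × 0.028 = 1.0 child.
- Highest: μ = 10.5, σ = 0.8 gives 0.334, and 36 × 0.334 = 12.0 children.

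These counts suppose no males aged 13 or over; with a share m of them, multiply by (1 − m).

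Distance to Grade 3 (below 8.5) in this group: a child in the row at 10.5 must fall by more than 10.5 − 8.5 = 2.0 g/dL. A Grade 1 child at 9.5 needs a fall of just over 9.5 − 8.5 = 1.0 g/dL but is outside the row.

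**5. Other analytes**

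The number removed is the share p with an abnormal baseline times 36. The documents give no p. As an assumed range, p = 10%, 20% and 30% give 3.6, 7.2 and 10.8 children.

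**The case against.** The strongest reply is that the shift tables do this job. For every Appendix 1.1 parameter, Hgb included, that is right. A reader might infer from the PCS rule that worsening from Grade 1-2 to Grade 3-4 is never counted; SAP 7.2 does not support that, because the shift tables are not limited by baseline. Hgb is also the primary endpoint and is summarized at every visit.

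A reader might also infer that the Hgb row must be empty. That follows only under the reference-range reading; under the ungraded reading it is sparse.

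Nor do the documents present the PCS table as the principal laboratory output. As written, it reports incidence among children with a normal baseline, which is what the protocol prespecified. To call that rate biased low presumes a different target; a lower count than under a worsening-based rule is to be expected but is not demonstrated.

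On the eight unscaled chemistries, the DAIDS table is not among the documents, so which of them it grades cannot be checked here. If Appendix 1.1 governs both the PCS and shift tables, the gap for these analytes comes from the missing scale, not the baseline rule. That stands, and the remedy must cover both causes.

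Finally, protocol 7.1 has clinically significant worsening recorded as an adverse event whatever the baseline, and the AESI search for hypophosphatemia has no baseline limit. That is a real safeguard, but it rests on investigator judgment. It does not cover non-serious anemia, which SAP 7.1 removes from adverse events.

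**Conclusion.** The point holds in a limited form and should be acted on. The PCS table omits all worsening from an abnormal baseline. For 8 chemistries and four hematology parameters the shift tables recover it. The Hgb PCS row will say little: about 0 of 36 children under one reading of *normal*, and roughly 1 to 12 of 36 under the other, given the assumed distributions and no males aged 13 or over.

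The material gap is in the unscaled chemistries, above all phosphorus. There, under either reading of which grades apply, no planned laboratory table is certain to count a child who starts abnormal and worsens to Grade 3-4. For the other seven the gap is conditional on DAIDS grading them. How many children are affected cannot be derived from the documents. The primary analysis is untouched.

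**What to change.** In SAP 7.2:

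- Define treatment-emergent PCS as a post-baseline Grade 3 or 4 value that is a higher grade than baseline. Use as denominator all participants with a baseline grade below 4 and at least one post-baseline value.
- Keep the normal-baseline subset as a second row, and state whether *normal* means the reference range or ungraded.
- Add to Appendix 1.1 the grades from the cited DAIDS table for phosphorus and for any other listed analyte that table grades, so that the PCS and shift tables cover the same analytes.
- Add a separate row to the phosphate time-course table for children with an abnormal baseline.
- Record the departure from protocol 8.5.4 in SAP Section 9. Protocol 9.8.5 allows changes in statistical methods to be documented in a plan.

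The cost is SAP wording, a longer appendix and minor programming. The downside is a possibly less favorable PCS count.

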7.3 VITAL SIGNS AND PHYSICAL EXAMINATION FINDINGS

7.3.1 Vital Signs

Vital signs will be collected including sitting body temperature, blood pressure (BP) and heart rate. On study drug dosing days BP and heart rate will be collected pre-dosing, immediately (within 5 minutes) post, and 30 minutes post dosing, and body temperature will be collected on each dosing day. The actual value and the change in vital signs (including sitting heart rate and blood pressure) from pre-infusion to each post-infusion time point will be summarized descriptively on each dosing day. Markedly abnormal values should be determined by PALS

Guidelines, 2015 in Appendix 1.2. Children >15 years of age will use the criteria for 15 years old children.

7.3.2 Physical Examination

Physical examination (PE) results were collected at Day 0 and Day 35 including six body systems, i.e. skin, cardiovascular, pulmonary/respiration, abdominal, central nervous system and musculoskeletal/extremities. Each component of the baseline physical examination will be recorded as normal or abnormal. Each component of the post baseline physical examinations will be recorded as No Change from Baseline PE or Change from Baseline PE. The number and percent of subjects who have normal, abnormal and significant changes at each visit will be summarized in table.

8. INTERIM ANALYSES AND DATA AND SAFETY MONITORING BOARD (DSMB)

8.1 INTERIM ANALYSES

No formal interim analysis is planned for this study.

8.2 DATA AND SAFETY MONITORING BOARD (DSMB)

No Data Safety Monitoring Board for this study.

9. SUMMARY OF MAJOR CHANGES IN THE PLANNED ANALYSES

Compared with the study protocol (03 December 2019 Administrative Change 1), below items are the major changes made in this SAP:

1. The LOCF imputation method was proposed for paired t-test for primary and secondary efficacy endpoints in SAP.
2. The scale defined in Division of AIDS (DAIDS) Table for Grading the Severity of Adult and Pediatric Adverse Events, Version 2.1 from March 2017 (Division of AIDS, National Institute of Allergy and Infectious Diseases, National Institutes of Health, US Department of Health and Human Services) will be used to identify abnormal clinical laboratory values instead of toxicity criteria from the National Cancer Institute Common Terminology Criteria version 5 for Adverse Events specified in the protocol.

10. APPENDICES

APPENDIX 1.1 ADVERSE EVENT SCALE

CHEMISTRIES Adverse Event Scale				
PARAMETER	GRADE 1 MILD	GRADE 2 MODERATE	GRADE 3 SEVERE	GRADE 4 POTENTIALLY LIFE- THREATENING
Albumin, Low (g/dL; g/L)	3.0 to < LLN 30 to < LLN	≥ 2.0 to < 3.0 ≥ 20 to < 30	< 2.0 < 20	NA
Alkaline Phosphatase, High	1.25 to < 2.5 x ULN	2.5 to < 5.0 x ULN	5.0 to < 10.0 x ULN	≥ 10.0 x ULN
ALT or SGPT, High Report only one	1.25 to < 2.5 x ULN	2.5 to < 5.0 x ULN	5.0 to < 10.0 x ULN	≥ 10.0 x ULN
AST or SGOT, High Report only one	1.25 to < 2.5 x ULN	2.5 to < 5.0 x ULN	5.0 to < 10.0 x ULN	≥ 10.0 x ULN
Calcium, High (mg/dL; mmol/L) ≥ 7 days of age	10.6 to < 11.5 2.65 to < 2.88	11.5 to < 12.5 2.88 to < 3.13	12.5 to < 13.5 3.13 to < 3.38	≥ 13.5 ≥ 3.38
Calcium, Low (mg/dL; mmol/L) ≥ 7 days of age	7.8 to < 8.4 1.95 to < 2.10	7.0 to < 7.8 1.75 to < 1.95	6.1 to < 7.0 1.53 to < 1.75	< 6.1 < 1.53
Creatinine, High Report only one	1.1 to 1.3 x ULN	> 1.3 to 1.8 x ULN OR Increase to 1.3 to < 1.5 x participant's baseline	> 1.8 to < 3.5 x ULN OR Increase to 1.5 to < 2.0 x participant's baseline	≥ 3.5 x ULN OR Increase of ≥ 2.0 x participant's baseline
Potassium, High (mEq/L; mmol/L)	5.6 to < 6.0 5.6 to < 6.0	6.0 to < 6.5 6.0 to < 6.5	6.5 to < 7.0 6.5 to < 7.0	≥ 7.0 ≥ 7.0
Potassium, Low (mEq/L; mmol/L)	3.0 to < 3.4 3.0 to < 3.4	2.5 to < 3.0 2.5 to < 3.0	2.0 to < 2.5 2.0 to < 2.5	< 2.0 < 2.0
Sodium, High (mEq/L; mmol/L)	146 to < 150 146 to < 150	150 to < 154 150 to < 154	154 to < 160 154 to < 160	≥ 160 ≥ 160
Sodium, Low (mEq/L; mmol/L)	130 to < 135 130 to < 135	125 to < 130 125 to < 130	121 to < 125 121 to < 125	≤ 120 ≤ 120

ULN and LLN required for the chemistries AE Scale (based on the high and low range from Covance Central Laboratory Services Manual, American Regent, Inc)								
Sex	Age	Alkaline Phosphatase LLN (U/L)	ALT ULN (U/L)	AST ULN (U/L)	Age	Creatinine ULN (mg/dL)	Age	Albumin LLN (g/dL)
Female	1-4 yr	<108	>34	>56	1-4 yr	>0.4	2 m-4 yr	<2.8
	4-7 yr	<96	>34	>48	4-7 yr	>0.5	4-16 yr	<2.9
	7-10 yr	<69	>34	>40	7-10 yr	>0.6	16-18 yr	<3.3
	10-15 yr	<51	>34	>40	10-13 yr	>0.7	18 yr	<3.3
	15-18 yr	<31	>34	>40	13-16 yr	>0.8		
	18 yr	<31	>34	>34	16-18 yr	>0.9		
					18 yr	>1.1		
Male	1-4 yr	<104	>34	>69	1-4 yr	>0.4	2 m-4 yr	<2.8

	4-7 yr	<93	>34	>59	4-7 yr	>0.5	4-16 yr	<2.9
	7-10 yr	<86	>34	>40	7-10 yr	>0.6	16-18 yr	<3.3
	10-15 yr	<95	>43	>40	10-13 yr	>0.7	18 yr	<3.3
	15-18 yr	<50	>43	>40	13-16 yr	>0.9		
	18 yr	<31	>43	>36	16-18 yr	>1.1		
					18 yr	>1.2		

HEMATOLOGY Adverse Event Scale				
PARAMETER	GRADE 1 MILD	GRADE 2 MODERATE	GRADE 3 SEVERE	GRADE 4 POTENTIALLY LIFE-THREATENING
Absolute Neutrophil Count (ANC), Low (cells/mm3; cells/L) > 7 days of age	800 to 1,000 0.800×10^9 to 1.000×10^9	600 to 799 0.600×10^9 to 0.799×10^9	400 to 599 0.400×10^9 to 0.599×10^9	< 400 $< 0.400 \times 10^9$
Hemoglobin, Low (g/dL; mmol/L) ≥ 13 years of age (male only)	10.0 to 10.9 6.19 to 6.76	9.0 to < 10.0 5.57 to < 6.19	7.0 to < 9.0 4.34 to < 5.57	< 7.0 < 4.34
≥ 13 years of age (female only)	9.5 to 10.4 5.88 to 6.48	8.5 to < 9.5 5.25 to < 5.88	6.5 to < 8.5 4.03 to < 5.25	< 6.5 < 4.03
57 days of age to < 13 years of age (male and female)	9.5 to 10.4 5.88 to 6.48	8.5 to < 9.5 5.25 to < 5.88	6.5 to < 8.5 4.03 to < 5.25	< 6.5 < 4.03
Platelets, Decreased (cells/mm3; cells/L)	100,000 to < 125,000 100.000×10^9 to < 125.000×10^9	50,000 to < 100,000 50.000×10^9 to < 100.000×10^9	25,000 to < 50,000 25.000×10^9 to < 50.000×10^9	< 25,000 $< 25.000 \times 10^9$
WBC, Decreased (cells/mm3; cells/L) > 7 days of age	2,000 to 2,499 2.000×10^9 to 2.499×10^9	1,500 to 1,999 1.500×10^9 to 1.999×10^9	1,000 to 1,499 1.000×10^9 to 1.499×10^9	< 1,000 $< 1.000 \times 10^9$

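### SAP Appendix 1.1 grades albumin values that its own limits table calls normal as moderate in children under 16, which distorts the shift tables; in-range creatinine rises need a wording repair and a flag

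*SAP*

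**What the plan says.** The chemistry scale in SAP Appendix 1.1 defines low albumin Grade 1 as "3.0 to < LLN 30 to < LLN" and Grade 2 as "≥ 2.0 to < 3.0 ≥ 20 to < 30", in g/dL and then g/L. Grade 3 is below 2.0 g/dL and there is no Grade 4. The Grade 2 band is absolute and does not mention the LLN.

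A second table follows, headed "ULN and LLN required for the chemistries AE Scale", so these limits are meant to be used with this scale. Its youngest row reads "1-4 yr >0.4 2 m-4 yr <2.8" and the next reads "4-7 yr >0.5 4-16 yr <2.9". In each, the first pair is the age band and high cut-off for creatinine (mg/dL), and the second pair is the age band and low cut-off for albumin (g/dL). From age 16 the albumin cut-off is 3.3.

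For creatinine, Grades 2 to 4 can be reached by a multiple of the ULN or, alternatively, by a multiple of the child's own baseline. The baseline route for Grade 3 is "Increase to 1.5 to < 2.0 x participant's baseline". Grade 4 is "≥ 3.5 x ULN OR Increase of ≥ 2.0" times the participant's baseline.

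SAP 7.2 uses the grades in two ways. Shift tables compare the baseline grade with the maximum post-baseline grade and with the last-visit grade. The PCS table counts Grade 3 or 4 at any post-baseline visit, among children with a normal baseline and at least one later value. Section 7.2 does not say what makes a baseline normal. I found no rule in the SAP that a value within limits is Grade 0.

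**The concern.** A grading scale and the normal limits supplied for it should agree on which values are normal. For albumin under age 16 they do not, and participants are aged 1 to 18. A table programmed literally would report an apparent shift to moderate when albumin has moved within the normal range. It could also hide a real change: a child who starts at 2.9 and falls below the LLN, but not below 2.0, stays at Grade 2 throughout. A programmer who instead checks the LLN first would produce a different table from the same data.

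The study is single-arm with a maximum of about 36 children, so no control group shows how often such artefacts arise by chance. A few spurious moderate shifts could be taken for an effect of treatment.

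Creatinine raises a related but weaker issue. Young children's values are so low that a single reporting step can be a large multiple of baseline.

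**Working it through.** The plan gives no figure of its own to reproduce here. The check applies the Appendix 1.1 cut-points to the Appendix 1.1 limits. A limit printed as <2.8 is read as low only below 2.8, and >0.4 as high only above 0.4. Results are assumed to be reported to 0.1, as the limits are.

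**Albumin (g/dL)**

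Grade 1 is the set of values from 3.0 up to, but not including, the LLN. The in-range values graded 2 run from the LLN up to, but not including, 3.0.

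| Age | LLN | Grade 1 band | In range but Grade 2 | At one decimal |
|---|---|---|---|---|
| 2 months to 4 years | 2.8 | 3.0 to <2.8: empty | 2.8 to <3.0 | 2.8, 2.9 |
| 4 to 16 years | 2.9 | 3.0 to <2.9: empty | 2.9 to <3.0 | 2.9 |
| 16 years and over | 3.3 | 3.0 to <3.3 | none | none |

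- Shift tables: under 16, a move from 3.0 to 2.9 is a change of 0.1 between two normal values, but it is tabulated as Grade 0 to Grade 2.
- PCS numerator: this needs Grade 3 or 4. Albumin Grade 3 is below 2.0, which is under every LLN (2.8, 2.9, 3.3), so no in-range albumin value can be counted.
- PCS denominator: a child under 16 with baseline 2.9 is included if normal means within laboratory limits, and excluded if it means Grade 0.

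**Creatinine (mg/dL), ages 1 to 4, ULN 0.4**

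- 0.2 to 0.3: 0.3/0.2 = 1.5 times baseline, which is Grade 3 and therefore PCS. Against the ULN, 0.3/0.4 = 0.75, so the value is within limits.
- 0.2 to 0.4: 0.4/0.2 = 2.0 times baseline; 0.4/0.4 = 1.0 times the ULN, again within limits. If the Grade 4 wording means a rise to at least 2.0 times baseline, this is Grade 4. If it means an added 2.0 times, the threshold is 1 + 2.0 = 3.0 times baseline, and values from 2.0 to below 3.0 times get no grade by this route.

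The 0.2 to 0.3 result is the same under both readings.

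**The case against.** The creatinine criterion is an explicit alternative in the chosen scale. It is built to catch relative rises wherever the ULN lies, so grading an in-range value follows from the scale and does not contradict the limits table. This stands.

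A reader might infer that such rises are non-events that Protocol 8.5.4 rules out, since it describes PCS as a case where the "baseline value is normal and post-baseline value is abnormal". The text does not support that. The same sentence goes on to explain abnormal as meeting Grade III or IV toxicity criteria, so the protocol defines it by grade and not by the ULN. SAP Section 9 openly replaces the protocol's toxicity criteria with the current scale. Nor would it be harmless to require a value above the ULN. In a male aged 16 to 18 (ULN 1.1), a rise from 0.5 to 1.1 is 1.1/0.5 = 2.2 times baseline and would go ungraded. In a male aged 13 to 16 (ULN 0.9), 0.4 to 0.9 is 0.9/0.4 = 2.25 times and would also be lost.

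The consequences are also limited. The laboratory tables are descriptive, and actual values and changes are summarized beside them. Under Protocol 7.1 a laboratory value becomes an adverse event only if it is outside normal limits and judged a clinically significant worsening, so in-range albumin does not reach the adverse event tables by that route. A child stable at 2.9 appears as Grade 2 to Grade 2, which is no shift. All of this is fair, but it does not remove the albumin contradiction.

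**Conclusion.** The albumin scale is wrong as written for children under 16: Grade 1 is empty and a narrow band of normal values is Grade 2. The band is 0.2 g/dL wide under age 4 (3.0 - 2.8) and 0.1 wide from 4 to 16 (3.0 - 2.9). The effect falls on the shift tables and, because a normal baseline is undefined, on the PCS denominator. The albumin result rests only on the appendix's own limits; one-decimal reporting matters just for listing the individual values.

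Three stronger conclusions might be drawn and should not be:

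- That albumin inflates the PCS count: it cannot, since Grade 3 starts below 2.0.
- That the tables will contain such cases: the documents give no frequencies, so the statement is that they can. One child of 36 would be 1/36 = 2.8%, but that is a scale for a single case and not an estimate.
- That 0.2 to 0.4 creatinine is certainly Grade 4: that depends on how the Grade 4 wording is read.

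For creatinine, what holds is an ambiguity of wording and a need for labelling, because a 0.1 step at low values can reach Grade 3 within the ULN (assuming reporting to 0.1).

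**What to change.** In SAP Appendix 1.1 and Section 7.2:

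1. State that albumin at or above the age-specific LLN is Grade 0. Under 16 years, Grade 2 is 2.0 to below the LLN and Grade 1 is not applicable. Ages 16 and over stay as they are.
2. Define a normal baseline in the PCS denominator as within the same laboratory limits.
3. Keep the baseline-multiple criterion for creatinine, but use one wording for Grades 3 and 4, so that it is clear whether the multiple is the level reached or the amount added, and so that no gap remains between the grades.
4. In the PCS and shift tables, mark by footnote or listing which Grade 3 or 4 creatinine values are within the age- and sex-specific ULN.

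Confine the in-range rule to albumin. A rule for every analyte would reach calcium, sodium, potassium and the hematology tests, for which Appendix 1.1 supplies no laboratory limits and no conflict has been shown.

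The cost is a few lines of SAP text, one programming condition and a flag. Data collection and the efficacy analyses are unaffected. The small downside is a departure from the literal published albumin scale, which should be stated in SAP Section 9.
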